3 STUDY OBJECTIVES AND ENDPOINTS

3.1 Objectives

Primary

- To demonstrate the efficacy in subjects with R/R T-PLL treated with venetoclax plus ibrutinib.

Secondary

- To assess safety and tolerability in subjects with T-PLL treated with venetoclax plus ibrutinib.
- To assess the ability of the subset of transplant-naïve subjects to proceed to further autologous/allogeneic stem cell transplantation (assessed by number of eligible subjects reaching transplant).
- To evaluate the PFS, duration of response, time-to-progression, event-free survival, disease control rate, and overall survival.

Exploratory

- To identify biomarker/genetically-defined subgroups regarding response and survival.

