3.3 Secondary Endpoints

Key secondary endpoints are as follows:

- PFS, defined as the time from the date of first dose of any study drug to the date of earliest disease progression or death
- duration of response, defined for subjects who achieve a best overall response of CR, CRi, or PR, as the time from the date of first response (CR, CRi, or PR) to the earliest date of disease progression or death
- time-to-progression, defined as the time from the date of first dose of any study drug to the date of earliest disease progression

- event-free survival, defined as the time from the date of first dose of any study drug to the date of earliest disease progression, death, or start of a new anti-T-PLL therapy
- disease control rate, defined as the proportion of subjects achieving CR, CRi, PR, or stable disease as best overall response
- overall survival, defined as the time from the date of first dose of any study drug to death from any cause
- number of eligible subjects reaching autologous or allogeneic transplantation; eligible subjects are the transplant-naïve subjects who have achieved CR

All secondary endpoints will be assessed per investigator assessment in R/R T-PLL subjects based on the T-PLL consensus criteria 2019.¹¹

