7.4 Statistical Analyses for Efficacy

The primary efficacy endpoint will be the ORR, defined as the proportion of subjects achieving CR, CRi, or PR as their best overall response in R/R T-PLL subjects as per investigator based on the T-PLL consensus criteria 2019.¹¹ The best overall response of CR/CRi/PR will be defined as achieving CR, CRi, and PR at any point during the study (CR/CRi will need confirmation assessment based on the T-PLL consensus criteria 2019).¹¹ The estimate and 90% confidence interval for ORR based on binomial distribution will be constructed. Subjects who have not achieved any component of ORR will be considered as nonresponders in the calculation of ORR at the time of analysis.

The secondary efficacy analysis will be based on the following endpoints: PFS, duration of response, time-to-progression, event-free survival, disease control rate, overall survival, and number of eligible subjects reaching autologous or allogeneic transplantation. All secondary endpoints will be assessed per investigator assessment in R/R T-PLL subjects based on the T-PLL consensus criteria 2019.¹¹

Time-to-event endpoints will be analyzed using Kaplan-Meier methodology. Median time-to-event and the corresponding 95% CI will be provided. Binary endpoints will be analyzed using binomial distribution and estimate of proportion along with 95% confidence interval will be provided.

Details on the primary and other efficacy analyses are provided in the SAP.

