3.11 Post-Treatment Follow-Up and Survival Visits

Subjects who discontinue study drug but have not experienced progressive disease (PD) will return for post-treatment follow-up visits. The post-treatment follow-up visits will follow the same schedule as the visit schedule (i.e., Week 4, Week 8, Week 12, Week 16, Week 24, Week 36, and every 12 weeks thereafter). Subjects will return for post-treatment follow-up visits until study completion starting from study drug discontinuation until documented PD or other post-treatment therapies (including stem cell transplantation) are received. Follow-up hematology and disease response assessment data will be collected.

Survival information (i.e., the date and cause of death) will be collected via telephone calls at 6-month intervals or as needed to allow for more frequent survival analyses.

All subjects will be followed for survival information (i.e., date and cause of death, all poststudy anticancer treatment including stem cell transplantation, reasons for poststudy anticancer treatment, regimens, dates of initiation and completion, etc.) unless the subject requests to be withdrawn from the

study survival follow-up; this request must be documented in the subject's medical record and signed by the investigator. If the subject withdraws from study follow-up, the study staff may use a public information source (such as county records) to obtain information about survival status only, as appropriate per local regulations.

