4.0 Study Background

4.1 Objective

Primary Objective:

The primary objective of this study is to evaluate the efficacy of venetoclax in combination with ibrutinib in subjects with relapsed or refractory (R/R) T-cell prolymphocytic leukemia (T-PLL). Efficacy will be measured by overall response rate (ORR) in R/R subjects.

Secondary Objectives:

- Secondary efficacy analyses will be performed by the following endpoints:
 - Progression-free survival (PFS)
 - Duration of response (DoR)
 - Time-to-progression (TTP)
 - Event-free survival (EFS)
 - Overall survival (OS)

- To assess safety and tolerability in subjects with T-PLL treated with venetoclax in combination with ibrutinib. Safety will be assessed by
 - Adverse event (AE) monitoring, physical examinations, vital sign measurements, electrocardiogram variables and clinical laboratory testing.
- To assess the ability of the subset of transplant-naïve subjects to proceed to further autologous/allogeneic stem cell transplantation, will be measured by
 - Total number of eligible subjects reaching autologous or allogeneic transplantation.

Exploratory Objective:

The exploratory objective is to identify biomarker/genetically-defined subgroups regarding response and survival. Types of biomarkers may include nucleic acids, proteins, lipids, or metabolites. These biomarker assessments may be used to assess and generate prognostic, predictive, pharmacodynamics, or surrogate biomarker signatures. Analyses of biomarkers may be done as an external study report and will not be a part of the clinical study report.

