4.3.2 Secondary Efficacy Endpoints

The following are the secondary efficacy endpoints in the study: PFS, DoR, TTP, EFS, OS, total number of eligible subjects (transplant-naïve subjects who have achieved CR) reaching autologous or allogeneic transplantation.

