For all the time-to-event endpoints (PFS, TTP, DoR, EFS and OS) a sensitivity analysis may be performed for the CR subjects who have undergone stem-cell transplantation by censoring them at their last disease assessment prior to the transplant.

Transplant-naïve subjects to proceed to further autologous/allogeneic stem cell transplantation will be measured by the - proportion of eligible subjects reaching autologous or allogeneic transplantation. The eligible subjects are defined as the transplant-naïve subjects who have achieved CR and then proceed to further autologous/allogeneic stem cell transplantation.

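### SAP 6.4 makes having the transplant part of being eligible for it, so its transplant proportion can only be 100% or undefined

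*SAP*

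**What the plan says.** The protocol treats the endpoint as a count. Under its secondary objectives (3.1), the ability of transplant-naïve subjects to go on to transplantation is "assessed by number of eligible subjects reaching transplant". Protocol 3.3 lists the endpoint and defines its terms: "number of eligible subjects reaching autologous or allogeneic transplantation; eligible subjects are the transplant-naïve subjects who have achieved CR".

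The SAP starts out the same way. SAP 4.1 gives the measure as "Total number of eligible subjects reaching autologous or allogeneic transplantation", and SAP 4.3.2 lists "total number of eligible subjects (transplant-naïve subjects who have achieved CR) reaching autologous or allogeneic transplantation".

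The analysis instruction differs. It is the second paragraph of SAP 6.4, under the Sensitivity Analysis heading. The measure there is the "proportion of eligible subjects reaching autologous or allogeneic transplantation", followed by this definition: "The eligible subjects are defined as the transplant-naïve subjects who have achieved CR and then proceed to further autologous/allogeneic stem cell transplantation".

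SAP 6.3 specifies analyses only for PFS, DoR, TTP, EFS and OS, so SAP 6.4 is the only place in the SAP that says how the transplant endpoint is to be analysed. Protocol 7.4 lists the endpoint among the secondary efficacy analyses and adds a general rule: "Binary endpoints will be analyzed using binomial distribution and estimate of proportion along with 95% confidence interval will be provided". It gives no denominator for this endpoint.

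**The concern.** A proportion meant to describe how often eligible subjects reach transplant needs a denominator fixed without reference to whether they were transplanted. SAP 6.4 puts the outcome into the eligibility definition, so a subject in CR who is never transplanted drops out of the denominator instead of counting as a failure.

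The count alone does not show how many subjects in CR did not go on to transplant. A proportion with the right denominator would show that; the SAP 6.4 proportion cannot. If the binary-endpoint rule of Protocol 7.4 is applied, this uninformative figure would also be given a confidence interval.

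SAP 6.4 also conflicts with SAP 4.3.2 in the same document, so two analysts following different sections would report different results from the same data.

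**Working it through.** The documents give no expected number of complete remissions or transplants, so there is no planned figure to reproduce. The check is a comparison of definitions, followed by an illustration.

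**Notation.** C is the number of transplant-naïve subjects who achieved CR. T is the number of those C who were then transplanted, so 0 ≤ T ≤ C.

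**The two definitions side by side**

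| Source | Who is eligible | Measure | Result |
|---|---|---|---|
| Protocol 3.3; SAP 4.3.2 | transplant-naïve and CR | number | T (as a proportion, T/C) |
| SAP 6.4 | transplant-naïve, CR and transplanted | proportion | T/T |

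Under SAP 6.4 the numerator is eligible subjects who were transplanted, which is T. The denominator is eligible subjects, which is also T because transplant is a condition of eligibility. Hence:

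- T ≥ 1: T/T = 100%, whatever C is.
- T = 0: 0/0, undefined.

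The two proportions agree only when T = C > 0, that is, when every eligible subject is transplanted.

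**Illustration.** Assume C = 6. Intervals are exact (Clopper-Pearson) at 95%. When all n subjects are successes, the lower limit is 0.025^(1/n): 0.025 for n = 1, 0.292 for n = 3 and 0.541 for n = 6. When none of n is a success, the upper limit is 1 − 0.025^(1/n), which is 0.459 for n = 6.

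| T | T/C, SAP 4.3.2 and Protocol 3.3 definition (95% CI) | T/T, SAP 6.4 (95% CI) |
|---|---|---|
| 0 | 0/6 = 0% (0–46%) | undefined |
| 1 | 1/6 = 17% (0.4–64%) | 1/1 = 100% (2.5–100%) |
| 2 | 2/6 = 33% (4–78%) | 2/2 = 100% (16–100%) |
| 3 | 3/6 = 50% (12–88%) | 3/3 = 100% (29–100%) |
| 4 | 4/6 = 67% (22–96%) | 4/4 = 100% (40–100%) |
| 5 | 5/6 = 83% (36–99.6%) | 5/5 = 100% (48–100%) |
| 6 | 6/6 = 100% (54–100%) | 6/6 = 100% (54–100%) |

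**Sensitivity to the assumed C.** The pattern does not depend on six. With C = 4 and T = 2, T/C is 50.0% (6.8–93.2%). With C = 8 and T = 2, it is 25.0% (3.2–65.1%). SAP 6.4 gives 2/2 = 100% (15.8–100%) in both cases.

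**The case against.** The strongest reply is that this is a drafting slip nobody would program. The paragraph opens by referring to transplant-naïve subjects, which echoes the objective, and the final clause may be numerator wording that has strayed into the definition. A workable definition stands in SAP 4.3.2, and SAP 3.0 leaves programming conventions to the Statistical Programming Plan, which is not available here.

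A slip is indeed the likely origin, but the text does not settle what was meant. The opening words could equally point to all transplant-naïve subjects as the denominator. Suppose 20 transplant-naïve subjects, 6 in CR and 3 transplanted (assumed numbers). The three readings give 3/20 = 15%, 3/6 = 50% and 3/3 = 100%. In an open-label trial, that choice should be made in the SAP and not during programming.

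Other objections hold in part:

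- **The specified endpoint is a count, and the count is intact.** Correct. Under SAP 6.4 a reader would still see 1/1 or 6/6. What is lost is the number in CR who were not transplanted.
- **Version lag.** SAP 3.0 refers to the protocol of 02 May 2019, and the amendment summary shows that the brief endpoint definitions in Protocol 3.3 were added in the later version. This weakens the conflict with the protocol, but not the one between SAP 4.3.2 and SAP 6.4.
- **Confidence interval.** SAP 6.4 attaches none, and Protocol 7.4 does not expressly class this endpoint as binary. That an interval would be reported is an inference.
- **Importance.** SAP 4.6 calls the study hypothesis generating, and this is one secondary endpoint. That limits the consequence, but does not make the stated rule usable.

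**Conclusion.** The concern holds. As written, the SAP 6.4 proportion is 100% whenever anyone is transplanted and undefined otherwise, and it contradicts SAP 4.3.2 and Protocol 3.3. This follows from the wording and needs no assumption about the data. The size of the distortion does depend on C and T, which the documents do not project. With an assumed C = 6, the reported figure would be 100% where the SAP 4.3.2 definition gives 17% (one transplanted) or 50% (three transplanted).

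The damage is confined to this one derived figure. The count T, the primary endpoint and the stage decisions are untouched. It should be corrected because a stated analysis rule yields an uninformative result, but it does not threaten the trial's main conclusion.

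**What to change.** In SAP 6.4, end the definition of eligible subjects at the achievement of CR and delete the rest of that sentence, so that it matches SAP 4.3.2 and Protocol 3.3. Then add one sentence: report the count T, which is the protocol's stated measure, together with T divided by the number of transplant-naïve FAS subjects who achieved CR, with an exact 95% CI. If no transplant-naïve subject achieves CR, report the count and state that the proportion cannot be calculated. Moving the paragraph from the Sensitivity Analysis heading to SAP 6.3 would also help, but is optional. The CR-based definition of eligible is left as it is.

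The cost is one clause deleted and a short reporting rule added, with no protocol amendment. No new data are needed: Operations Manual 3.2 already records treatments in the oncology history, and Operations Manual 3.11 collects "all poststudy anticancer treatment including stem cell transplantation". The downside is that the reported proportion may fall below 100%, and its interval will be wide if few subjects reach CR.

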6.5 Efficacy Subgroup Analyses

The subgroup analyses will be performed for ORR (overall response rate) for the full analysis set defined in Section 5.2. Subgroup analyses will be detailed in the SPP.

7.0 Safety Analyses

7.1 General Considerations

A safety analysis will be performed for all subjects who take at least one dose of study drug (venetoclax or ibrutinib). Safety evaluations include but are not limited to capturing adverse events (AEs), clinical laboratory testing (hematology and chemistry), vital sign measurements, electrocardiogram (ECG) testing (as clinically indicated), as a measure of safety and tolerability for the entire study duration. Throughout the study, AEs will be evaluated by the NCI-CTCAE v. 5.0 and summarized. Laboratory test results, vital signs and ECG assessments will be analyzed as appropriate.

7.2 Analysis of Adverse Events

All summaries/analyses involving AEs will include treatment-emergent adverse events (TEAE) only, unless otherwise specified. TEAE are defined as any event with onset after the first dose of study drug and no more than 30 days after the last dose of study drug. Events where the onset date is the same as the study drug start date are assumed to be treatment-emergent, unless the study drug start time and the AE start time are collected and the AE start time is prior to the study drug start time. If an incomplete onset date was collected for an AE, the AE will be assumed to be treatment-emergent unless there is evidence that confirms that the AE was not treatment-emergent (e.g., the AE end date was prior to the date of the first dose of study drug).

For summaries of AEs related (reasonable possibility) to study drug, at each level of summation (overall, SOC, and PT) each subject is counted only once. If a subject has an AE with unknown relationship, then the subject will be counted in the relationship category of "unknown," even if the subject has another occurrence of the same event with a relationship of "no reasonable possibility" present. The only exception is if the subject has another occurrence of the same AE with the relationship of "reasonable possibility." In this case, the subject will be counted under the reasonable possibility category.

Adverse event data will be summarized and presented using primary MedDRA system organ classes (SOCs) and preferred terms (PTs) according to the MedDRA coding dictionary version 21.0 or higher.

The number and percentage of subjects experiencing treatment-emergent adverse events will be summarized for the following adverse event summaries:

- Any treatment-emergent adverse event.
- Any treatment-emergent adverse event with NCI toxicity (CTCAE version 5.0) grade 3, 4, or 5 adverse events.
- Any treatment-emergent adverse event with NCI toxicity (CTCAE version 5.0) grade 3 or 4 adverse event.
- Adverse events broken down by NCI toxicity grade (Severity).
- Any treatment-emergent serious adverse event.
- Any treatment-emergent adverse event leading to discontinuation of venetoclax.
- Any treatment-emergent adverse event leading to venetoclax interruption.
- Any treatment-emergent adverse event leading to venetoclax reduction.
- Any treatment-emergent adverse event that is rated at least possibly related to venetoclax by the investigator (Reasonable Possibility Related)
- Any treatment-emergent adverse event leading to discontinuation of ibrutinib.
- Any treatment-emergent adverse event leading to ibrutinib interruption.
- Any treatment-emergent adverse event leading to ibrutinib reduction.
- Any treatment-emergent adverse event that is rated at least possibly related to ibrutinib by the investigator (Reasonable Possibility Related)
- Any treatment-emergent adverse event leading to death.

In addition, selected adverse events will be summarized. The list of such events is shown in [Table 2](#).

Table 2. Selected Adverse Events

Risk	Search Criteria
Tumor Lysis Syndrome (TLS)	SMQ – "Tumour lysis syndrome" (Narrow-scope)
Neutropenia	PT terms – "Neutropenia," "Neutrophil count decreased," "Febrile neutropenia," "Agranulocytosis," "Neutropenic infection," and "Neutropenic sepsis"
Serious Infection, Including Opportunistic Infections	SAEs in the SOC of "Infections and Infestations"
Second Primary Malignancy	SMQ – "Malignant tumours" (Narrow) and "Myelodysplastic syndromes" (Narrow)
Lymphopenia	PT terms – "Lymphopenia" and "Lymphocyte count decreased"
Anemia	PT terms – "Anaemia" and "Haemoglobin decreased"
Thrombocytopenia	PT terms – "Thrombocytopenia" and "Platelet count decreased"
Drug Induced Liver Injury (DILI)	SMQ – "Drug related hepatic disorders – comprehensive search"
Medication Error	SMQ – "Medication error" (broad)
Hemorrhage	SMQ – "Haemorrhagic disorders" (narrow)

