Congenital Anomaly	An anomaly detected at or after birth, or any anomaly that results in fetal loss.
Persistent or Significant Disability/Incapacity	An event that results in a condition that substantially interferes with the activities of daily living of a study subject. Disability is not intended to include experiences of relatively minor medical significance such as headache, nausea, vomiting, diarrhea, influenza, and accidental trauma (e.g., sprained ankle).
Important Medical Event Requiring Medical or Surgical Intervention to Prevent Serious Outcome	An important medical event that may not be immediately life-threatening or result in death or hospitalization, but based on medical judgment may jeopardize the subject and may require medical or surgical intervention to prevent any of the outcomes listed above (i.e., death of subject, life-threatening, hospitalization, prolongation of hospitalization, congenital anomaly, or persistent or significant disability/incapacity). Additionally, any elective or spontaneous abortion or stillbirth is considered an important medical event. Examples of such events include allergic bronchospasm requiring intensive treatment in an emergency room or at home, blood dyscrasias or convulsions that do not result in inpatient hospitalization, or the development of drug dependency or drug abuse.

All AEs reported from the time of study drug administration until 30 days after discontinuation of study drug administration will be collected, whether solicited or spontaneously reported by the subject. In addition, protocol-related SAEs and protocol-related nonserious AEs will be collected from the time the subject signs the study-specific informed consent.

The following definitions will be used for a Serious Adverse Reaction (SAR) and Suspected Unexpected Serious Adverse Reaction (SUSAR):

SAR	Defined as all noxious and unintended responses to an Investigational Medicinal Product (IMP) related to any dose administered that result in an SAE as defined above.
SUSAR	A suspected SAR: refers to individual SAE case reports from clinical trials where a causal relationship between the SAE and the IMP was suspected by either the sponsor or the investigator, is not listed in the applicable Reference Safety Information, and meets one of the above serious criteria. All individually reported SARs are considered suspected.

AbbVie will be responsible for SUSAR reporting for the IMP in accordance with global and local requirements.

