6.2 Toxicity Management

The management of specific AEs and laboratory parameters is described below. This includes AEs of TLS, major hemorrhage, and neutropenia for venetoclax and known potential risks associated with ibrutinib.

Tumor lysis syndrome: There is a potential for TLS in subjects affected by hematologic malignancies. Depending on the specific tumor type, risk factors may include one or more of the following: bulky disease or high tumor burden, renal insufficiency, splenomegaly, elevated pretreatment lactate dehydrogenase levels, elevated leukocyte count, and dehydration.

Venetoclax can cause rapid reduction in tumor and thus poses a risk for TLS. Changes in electrolytes consistent with TLS that require prompt management can occur as early as 6 to 8 hours following the first dose of venetoclax ([Appendix E](#)). Potassium increases can be life-threatening and should be treated as an emergency. Definitions of laboratory TLS and clinical TLS are provided in the [Appendix D](#) (Howard grading classification). Due to the short dose ramp-up used in this study, all subjects will be managed as high risk for TLS. If a subject experiences blood chemistry changes suggestive of TLS, the dose of venetoclax should be withheld and reductions may be required ([Appendix F](#)).

Major hemorrhage: Fatal bleeding events have occurred in patients treated with ibrutinib. A major hemorrhage is any hemorrhagic AE of Grade 3 or higher; any SAE of bleeding of any grade; or any

central nervous system hemorrhage/hematoma of any grade. All hemorrhagic AEs requiring a transfusion of red blood cells should be reported as a Grade 3 or higher per NCI-CTCAE. Ibrutinib may be withheld and/or reductions may be required.

Neutropenia: Venetoclax may cause neutropenia. Subjects with a history of neutropenia who have received multiple prior therapies and/or have significant bone marrow involvement may be at a particularly high risk. Grade 3 or 4 neutropenia has been reported in subjects treated with venetoclax. Subjects will be managed for neutropenia as detailed below.

Known potential risks associated with ibrutinib are listed below, and treatment may be discontinued or adjusted in response to occurrence of these events, as appropriate. Please refer to the ibrutinib Investigator's Brochure⁹ for additional information on potential risks for ibrutinib.

- hemorrhage, infections, cytopenias, cardiac arrhythmias, hypertension, second primary malignancies, and TLS

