Subjects will be monitored for these events throughout the study and treatment may be discontinued or adjusted as appropriate.

Prophylaxis and Management of Tumor Lysis Syndrome

The risk of TLS is a continuum based on multiple factors including tumor burden, CrCL, and other comorbidities. Subjects with high tumor burden (e.g., any lymph node with a diameter > 5 cm or ALC > 25 × 10⁹/L) are at greater risk of TLS when initiating venetoclax. Reduced renal function (CrCL < 80 mL/min) further increases the risk. The risk may decrease as tumor burden decreases with venetoclax treatment. Tumor burden categories are provided in [Table 3](#).

Prior to initiating venetoclax, tumor burden assessment, including radiographic evaluation (e.g., CT scan), should be performed for all subjects during screening. In addition, blood chemistry (potassium, calcium, phosphorus, uric acid, and creatinine) assessments should be performed in all subjects at screening with correction of pre-existing abnormalities.

Table 3. Tumor Burden Categories

Tumor Burden Category	Criteria
Low	• All measurable lymph nodes with the largest diameter < 5 cm AND ALC < 25 × 10 ⁹ /L
Medium	• Any measurable lymph node with the largest diameter ≥ 5 cm and < 10 cm OR ALC ≥ 25 × 10 ⁹ /L
High	• Any measurable lymph node with the largest diameter ≥ 10 cm OR ALC ≥ 25 × 10 ⁹ /L AND any measurable lymph node with the largest diameter ≥ 5 cm but < 10 cm

ALC = absolute lymphocyte count

All subjects will be hospitalized for close monitoring and prophylaxis during the venetoclax dose ramp-up, starting 1 day prior to venetoclax initiation until 1 day after reaching target dose of venetoclax (400 mg QD).

All TLS prophylaxis measures should be appropriately recorded in the eCRF.

Hydration: All subjects, regardless of risk for TLS, should be adequately hydrated before starting treatment with venetoclax and during the dose ramp-up phase. The recommended volume is 1.5 to 2.0 L (approximately 6 to 8 glasses) of water each day. Subjects should be instructed to drink water at least 48 hours before and on the day of the first dose. Intravenous (IV) fluids should be administered (i.e., 150 – 200 mL/hour) daily, as tolerated, during the hospitalization period.

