Bone marrow sample for optional biomarker assessments to be collected for subjects who provided consent for the relative studies AND if a bone marrow sample is collected to confirm CR/CRi or collected per standard-of-care.

Survival Follow-Up:

 INTERVIEW	Survival assessment	Any new anticancer therapy
---	---------------------	----------------------------

NOTES: Subjects who discontinue the study drug and are no longer in post-treatment follow-up should be contacted every 6 months by telephone for survival assessment and for information on new anticancer therapies.

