4 SAFETY MANUAL

4.1 Methods and Timing of Safety Assessment

All protocol-related serious adverse events (SAEs) as well as protocol-related nonserious AEs (e.g., infection at liver biopsy site done during screening) will be collected from the time the subject signed the study-specific informed consent until study drug administration. From the time of study drug administration until 30 days after discontinuation of study treatment, all AEs and SAEs will be collected whether solicited or spontaneously reported by the subject. After 30 days following completion of study treatment and throughout the post-treatment period, all spontaneously reported SAEs will be collected (nonserious AEs will not be collected). All AEs should be followed until resolution, return to baseline, or determined to be stable per the investigator.

AE = adverse event; SAE = serious adverse event

a. 30 Days after the last dose of venetoclax or ibrutinib.

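### Second primary malignancy is to be monitored throughout the study, but the SAP counts it only to 30 days after last dose and gives later serious events no output

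*SAP*

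**What the plan says.** **The risk and its monitoring.** Protocol 6.2 lists the known potential ibrutinib risks as "hemorrhage, infections, cytopenias, cardiac arrhythmias, hypertension, second primary malignancies, and TLS". It then says: "Subjects will be monitored for these events throughout the study and treatment may be discontinued or adjusted as appropriate". SAP 7.1 describes safety as assessed over the whole study. Protocol 11 ends the study at the last subject's last visit or last follow-up contact, whichever is later.

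**Collection.** Protocol 6.1: "All AEs reported from the time of study drug administration until 30 days after discontinuation of study drug administration will be collected". Operations Manual 4.1 (in Appendix I of the protocol) goes further: "After 30 days following completion of study treatment and throughout the post-treatment period, all spontaneously reported SAEs will be collected". It adds that nonserious events are not collected in that period. Operations Manual 2.2 lists an adverse event assessment at post-treatment follow-up visits, which stop at progression or at the next therapy, transplant included. Subjects past that point "should be contacted every 6 months by telephone for survival assessment and for information on new anticancer therapies". Operations Manual 3.11 adds cause of death and "all poststudy anticancer treatment including stem cell transplantation, reasons for poststudy anticancer treatment".

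**Analysis.** SAP 7.2: "All summaries/analyses involving AEs will include treatment-emergent adverse events (TEAE) only, unless otherwise specified". It defines treatment-emergent as onset after first dose and no more than 30 days after last dose. SAP Table 2 includes a second primary malignancy row, defined by two narrow MedDRA queries, with no window of its own.

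**The concern.** The protocol treats second primary malignancy as a risk to watch for the length of the study, and it can appear after treatment has stopped. The planned analysis follows it only for time on drug plus 30 days. A case reported as an SAE in month 6 after stopping would be collected, yet the second primary malignancy row of the safety report could still read zero. The same applies to late serious infections and serious hemorrhages, which also have rows in Table 2.

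Collection has a narrower weakness. Once a subject progresses, is transplanted or starts another therapy, no scheduled contact asks directly about a second cancer. Transplant-eligible subjects stop the combination after reaching complete remission, so those who do best on treatment pass into this group.

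At stake is what the secondary safety objective can report on a named risk. The primary endpoint and the futility rule are untouched.

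**Working it through.** The plan gives no figure on this point to reproduce. The check follows second primary malignancy from the protocol's commitment through collection to output.

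| Period | Route into the data | Output in the SAP |
|---|---|---|
| First dose to 30 days after last dose | All adverse events (Protocol 6.1; Operations Manual 4.1) | Table 2 row and treatment-emergent summaries |
| After 30 days, no progression or new therapy | Adverse event assessment at post-treatment visits (Operations Manual 2.2); SAEs if spontaneously reported (4.1) | None named |
| After progression, transplant or new therapy | 6-monthly call on survival and new anticancer therapy (2.2), with cause of death and reasons for treatment (3.11); SAEs if spontaneously reported (4.1) | None named |

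Two further readings matter.

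1. The phrase allowing other specification in SAP 7.2 is not taken up for Table 2. It could have been: SAP 7.3 lifts the 30-day limit for the listings of grade 3 to 4 laboratory values.
2. A second malignancy that meets no seriousness criterion has no clear route after 30 days. Post-treatment visits list an adverse event assessment, but Operations Manual 4.1 says nonserious events are not collected then.

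**How much follow-up lies outside the window.** The documents give a maximum planned treatment of 2 years for transplant-ineligible subjects, but no expected time on drug and no follow-up length. The times below are therefore assumptions. With T months on drug and F months followed:

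share inside = (T + 30/30.4375) / F, where 30/30.4375 = 0.986 month.

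| T | F | Share inside | Share outside |
|---|---|---|---|
| 3 | 36 | 3.986/36 = 11% | 89% |
| 3 | 24 | 3.986/24 = 17% | 83% |
| 6 | 24 | 6.986/24 = 29% | 71% |
| 12 | 36 | 12.986/36 = 36% | 64% |
| 12 | 24 | 12.986/24 = 54% | 46% |
| 24 | 36 | 24.986/36 = 69% | 31% |

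These are shares of follow-up time. They are shares of events only if the hazard is constant.

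**What the study could show at best.** With complete ascertainment and no event in 37 subjects, the one-sided 95% upper limit for the proportion affected is 1 − 0.05^(1/37) = 7.8%. The value of a later count lies in complete reporting of individual cases; it cannot give a precise rate.

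**The case against.** A window of last dose plus 30 days is conventional, and it limits confounding by transplant and later treatment. The monitoring sentence in Protocol 6.2 sits under toxicity management and goes on to speak of adjusting treatment, so it can be read as on-treatment monitoring. Second primary malignancy is not among the adverse events of special interest in Protocol 6.1. The SAP also leaves programming conventions to a Statistical Programming Plan, which is not available here and might contain a late-SAE listing.

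The window is reasonable for the treatment-emergent tables and should stay there. It does not explain why a named risk has no second count, when SAP 7.1 speaks of the whole study and SAP 7.3 already lifts the limit for one set of listings. A listing that exists only in the programming plan would still be worth stating in the SAP.

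A reader might also infer more than the documents support:

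- **That nobody asks after day 30.** Subjects without progression or new therapy have an adverse event assessment at post-treatment visits. The gap in direct questioning applies only afterwards. Even then, cause of death and reasons for new anticancer treatment may reveal some cases, though neither is a defined second-malignancy item. Protocol 4.1 says transplanted subjects are followed for progression, but it attaches no adverse event assessment to that.
- **That Protocol 6.1 and Operations Manual 4.1 conflict.** They are complementary: the second repeats the 30-day rule and adds later SAEs.
- **That late SAEs are thrown away.** They are collected. What is missing is a planned output.
- **That a number of missed malignancies can be given.** Any such number needs an event rate and survival times that the documents do not contain. It would also count events outside the window, some of which would still be collected.

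**Conclusion.** The concern holds in two parts. The analysis part is firm: under SAP 7.2 the second primary malignancy row stops 30 days after last dose, and SAEs collected later have no named summary or listing. The collection part is limited to subjects past progression, transplant or new therapy, for whom the call has no direct item, and to nonserious cases after 30 days.

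Under the assumed times, 31% to 89% of follow-up lies outside the window. The expected number of events is small in a study of at most 37 subjects, in a disease the protocol describes as having short survival. The point is worth acting on because the change is cheap and alters what the safety report shows about a named risk. It does not affect the efficacy conclusions.

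**What to change.** 1. **SAP 7.2.** Keep the treatment-emergent count in the second primary malignancy row of Table 2. Beside it, report the count over all follow-up: number of subjects, time from first dose, and whether onset was before or after transplant or other therapy.
2. **SAP 7.2.** Add a listing of all SAEs with onset more than 30 days after last dose.
3. **Operations Manual 2.2.** Add one second primary malignancy item (yes/no, date, type) to the existing 6-monthly call, and record the same item at post-treatment visits regardless of seriousness.

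The cost is a few lines of SAP text, one eCRF item at contacts already scheduled, one extra set of table entries and one listing. No visit is added and the treatment-emergent tables stay as they are. The downside is interpretive: in a single-arm study, a cancer found after transplant or later treatment may not be attributable to study drug. Those events should be shown separately and not pooled with on-treatment cases.
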